1. OBJECTIVES AND ENDPOINTS

1.1 Objectives

- 1.1.1 Primary: To determine the effects of different daily doses of ibrutinib (420 mg, 280 mg, 140 mg) on free drug and chemokine levels in plasma, BTK occupancy by ibrutinib, BTK mRNA, BTK phospho- and total protein levels, downstream signaling, NF- κ B activity and platelet functionality.
- 1.1.2 Secondary: To observe the effects of different daily doses of ibrutinib (420 mg, 280 mg, 140 mg) on clinical parameters in patients with CLL in terms of efficacy and safety.

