1.2 Endpoints

- 1.2.1 Primary: Ibrutinib plasma and chemokine concentrations, BTK occupancy by ibrutinib, BTK mRNA levels, BTK phospho- and total protein levels, downstream signaling, NF- κ B p65 levels and platelet functionality on days 1 (baseline), 8 and 28 of each cycle of treatment.
- 1.2.2 Secondary: Absolute lymphocyte count (ALC), hemoglobin and platelet levels, CLL-related symptoms, and palpable lymphadenopathy and/or hepatosplenomegaly on day 28 of each cycle of treatment; characterization of safety and tolerability of ibrutinib throughout the study.

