 [name]
 [name]
 [contact]
 [contact]
 Email: [contact]

For the BTK occupancy assay, peripheral blood mononuclear cells from blood collected from patients will be isolated in [name] laboratory. The frozen cell pellets then will be transported on dry ice to Pharmacyclics (at the address indicated below). All patient samples are de-identified and neither the hospital number nor the names are included. Laboratories within Pharmacyclics will analyze these samples for the BTK occupancy assay.

Pharmacyclics LLC
 [name]
 [name].

Study Calendar

	Pre- Study	Wk 1	Wk 2	Wk 3	Wk 4	Wk 5	Wk 6	Wk 7	Wk 8	Wk 9	Wk 10	Wk 11	Wk 12
Ibrutinib		A	A	A	A	A	A	A	A	A	A	A	A
Informed consent	X												
Demographics	X												
Medical history	X												
Concurrent meds	X	X-----X											
Physical exam	X				X ^f				X ^f				X ^f
Vital signs	X				X ^f				X ^f				X ^f
Height	X												
Weight	X				X ^f				X ^f				X ^f
Performance status	X				X ^f				X ^f				X ^f

CBC w/diff, plts	X				X ^f				X ^f				X ^f
Serum chemistry ^a	X				X ^f				X ^f				X ^f
Serum beta-2-microglobulin	X				X ^f				X ^f				X ^f
IgG, IgA and IgM levels	X				X ^f				X ^f				X ^f
ECG	X				X ^f				X ^f				X ^f
Adverse event evaluation		X-----X											
β-HCG	X ^b												
Urinalysis	X												
Plasma ibrutinib and chemokine levels		X ^c	X ^d		X ^e	X ^c	X ^d		X ^e	X ^c	X ^d		X ^e
BTK occupancy levels		X ^c	X ^d		X ^e	X ^c	X ^d		X ^e	X ^c	X ^d		X ^e
BTK mRNA, protein and downstream signaling		X ^c	X ^d		X ^e	X ^c	X ^d		X ^e	X ^c	X ^d		X ^e
NF-κB activation assay		X ^c	X ^d		X ^e	X ^c	X ^d		X ^e	X ^c	X ^d		X ^e
Platelet functionality assay		X ^g			X ^g	X ^g			X ^g	X ^g			X ^g

A: Ibrutinib, orally daily, 420 mg/d in cycle 1 (weeks 1-4), 280 mg/d in cycle 2 (weeks 5-8), 140 mg/d in cycle 3 (weeks 9-12).

a: Albumin, alkaline phosphatase, total, direct and indirect bilirubin, bicarbonate, BUN, calcium, chloride, creatinine, glucose, LDH, phosphorus, potassium, total protein, SGOT [AST], SGPT [ALT], sodium.

b: Serum or urine pregnancy test (women of childbearing potential).

c: On day 1 of each cycle, samples at 0 (cycle 1 only), 4, and 24 hours (see appendix C). Please note that the day 1 time zero collection in cycles 2 and 3 coincides with the day 28 24-hour collection of the previous cycles; therefore, no separate day 1 time zero collection is required in cycles 2 and 3.

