- d. On day 8 of each cycle, samples at 4 and 24 hours (see appendix C).
- e. On day 28 of each cycle, samples at 24 hours (see appendix C).
- f. On day 28 (± 2 days) of each cycle.
- g. Pre-treatment (cycle 1 day 1) and 24 hours post-dosing on days 1 and 28 of each cycle.

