Previous clinical experience has shown that lower than standard doses of Ibrutinib have similar efficacy and lower toxicities. In a phase I study of ibrutinib in a different population of patients (with relapsed or refractory B-cell malignancies), BTK occupancy $\geq 95\%$ was achieved 4 hours post-dose in all patients receiving 2.5 mg/kg/day,⁶⁰ which equals 175 mg/day for patients weighing 70 kg. In total, 56 patients were enrolled onto this study with 7 dose levels, and 6 to 9 patients at each dose level, to provide data on means (SDs) of the concentration of ibrutinib over time, areas under the curves (AUCs) of the receiver operating characteristics (ROCs), BTK occupancy (in %) for different dose levels over time, and other PK/PD parameters. For the 7 dose levels, the mean AUCs over 0-24 hours range roughly from 100 to 1500 ng x h/mL, with their SDs ranging roughly from 20 to 400 ng x h/mL, and higher dose levels had larger mean AUCs and larger SDs. For the highest dose level, the mean (SD) concentrations of ibrutinib were roughly 20 (5), 100 (35), 135 (45), 55 (15) ng/mL at 1, 2, 3, and 4 hours after taking the drug. These data show that the sample sizes of 6 to 9 patients at each dose level are sufficient to provide reasonably accurate estimates for these PK/PD parameters. This pilot study will enroll up to 12 patients, but have each patient receive all the three proposed dose levels, one at a time, as described above.

We will also observe the effects of different daily doses of ibrutinib (420 mg, 280 mg, 140 mg) on clinical parameters in patients with CLL in terms of efficacy and safety. We will measure the absolute lymphocyte count (ALC), hemoglobin and platelet levels, CLL-related symptoms, and palpable lymphadenopathy and/or hepatosplenomegaly on day 28 of each cycle of treatment. We will characterize the safety and tolerability of ibrutinib throughout the study. Descriptive statistics will be used. Continuous variables e.g., clinical characteristics such as CBC parameters, and laboratory correlates such as plasma drug levels, BTK occupancy, mRNA and protein levels, and NF- κ B activity levels, will be summarized using the mean (SD) and/or median (range). Frequency tables will be used to summarize categorical variables.

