APPENDIX C. Pharmacodynamic Investigations

The objectives of the pharmacodynamic investigations during this clinical trial are as follows:

To determine the effects of different daily doses of ibrutinib (420 mg, 280 mg, 140 mg) on free drug levels in plasma, BTK occupancy by ibrutinib, BTK mRNA, BTK phospho- and total protein levels, B-cell receptor down-stream signaling targets, NF- κ B activity and platelet functionality such as Syk protein activation.

All patients will be investigated as this clinical trial is designed with pharmacodynamics as the primary investigation. Patients will sign consent forms to enter these investigations. Once a patient has consented to participate in the investigation, please contact [name] [contact]) or [name] office [contact]) in the Department of Experimental Therapeutics. Please collect blood samples as indicated below in green- or yellow-top tubes at the following times.

Pre-Dose (Pretreatment sample) (two green top tubes, one yellow top tube)

Cycle 1,2,3, Day 1 - 4 hr (one green top tube) and 24 hr (two green top tubes, one yellow top tube)

Cycle 1,2,3, Day 8 - 4 hr (one green top tube) and 24 hr (two green top tubes)

Cycle 1,2,3, Day 28 - 24 hr (two green top tubes, one yellow top tube)

Each blood sample (~10 ml) will be collected in a Vacutainer green top tube. The samples will be mixed and immediately put on ice-bath. Blood tubes will be picked up by [name] laboratory personnel and further processed to isolate plasma, platelets and CLL lymphocytes. Plasma will be used for ibrutinib pharmacology and for cytokine/chemokine assays; while platelets and lymphocytes will be used for protein and mRNA assays.

Plasma pharmacology: Ibrutinib levels will be quantitated by high performance liquid chromatography with tandem mass spectrometric detection at 4 and 24 hours post-dosing on days 1, 8, and 28 (but before the first dose of the next cycle) of each cycle. Exception: there will be no 4-hour blood draw on day 28.

Chemokine profiling: Plasma will be used to quantitate changes in CCL3, CCL4, and SDF1 levels.

BTK occupancy assay: This will be done using fluorescent affinity probe detection in pretreatment and at 4 and 24 hours post-dosing on days 1, 8, and 28 (but before the first dose of the next cycle). Exception: there will be no 4-hour blood draw on day 28.

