Measurement of platelet functionality: Syk protein activation will be evaluated in platelets isolated 24 hours post-treatment on days 1 and 28 of each cycle to determine if changes occur with different doses of ibrutinib during therapy.

Molecular profiling: The lymphocytes obtained in real-time during pre- and post-therapy will be saved and later sent for molecular profiling to determine a spectrum of total and phosphoproteins that have significance in CLL as well as in the B-cell receptor pathway.

BTK downstream pathway analysis: The leukemic lymphocytes will be washed, pelleted and saved to determine the decrease in target proteins BTK, pBTK (Tyr²²³) and downstream ERK, pERK(Thr²⁰²/Tyr²⁰⁴), AKT, pAKT (ser⁴⁷³) and NK-kB. Additional studies may be done to determine other downstream pathway molecules.

RT-PCR assays: To determine if changes in protein levels (identified during immunoblot assays) are due to changes in transcript levels, we will do RT-PCR assays on these samples.

References

1. Hallek M. Chronic lymphocytic leukemia: 2015 Update on diagnosis, risk stratification, and treatment. *Am J Hematol.* 2015;90(5):446-460.
4. Jain N and O'Brien S. Initial treatment of CLL: integrating biology and functional status. *Blood.* 2015;126(4):463-470.
8. Ponader S and Burger JA. Bruton's tyrosine kinase: from X-linked agammaglobulinemia toward targeted therapy for B-cell malignancies. *J Clin Oncol.* 2014;32(17):1830-1839.

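### Section 11 summarises the primary laboratory markers as levels only, so the change from each patient's untreated sample has no within-patient SD or confidence interval, and Appendix C omits the pretreatment Syk assay

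*Combined protocol and SAP*

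**What the plan says.** The primary objective (Section 1.1.1) is "To determine the effects of different daily doses of ibrutinib (420 mg, 280 mg, 140 mg) on free drug and chemokine levels in plasma" and on a list of further laboratory markers. Section 1.2.1 makes these primary endpoints and times them, ending with "platelet functionality on days 1 (baseline), 8 and 28 of each cycle of treatment".

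Patients have never had ibrutinib (exclusion 5.2.1). Study Calendar footnote c sets the draws for the blood markers: "On day 1 of each cycle, samples at 0 (cycle 1 only), 4, and 24 hours (see appendix C". The same footnote says that time zero in cycles 2 and 3 is the 24-hour sample after day 28 of the preceding cycle. The only drug-free sample is therefore the cycle 1 day 1 pre-dose draw.

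Section 11 plans a t-test of BTK occupancy at each dose. For continuous variables in general, with laboratory correlates among the examples, it says that they "will be summarized using the mean (SD) and/or median (range". It mentions no change, ratio, paired analysis or confidence interval. Its examples do not include chemokines, downstream signalling or platelet function.

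Appendix C shows that comparison with untreated values is intended. For chemokines it says "Plasma will be used to quantitate changes in CCL3, CCL4, and SDF1 levels", and for BTK and its downstream proteins it speaks of finding a decrease. It gives no reference time and no statistic.

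For platelets, Section 8.10 asks for a pre-dose measurement and footnote g for "Pre-treatment (cycle 1 day 1) and 24 hours post-dosing on days 1 and 28 of each cycle". The assay paragraph of Appendix C says only that "Syk protein activation will be evaluated in platelets isolated 24 hours post-treatment on days 1 and 28 of each cycle".

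**The concern.** An effect of a dose on a marker such as phospho-BTK or CCL3 needs a reference, and the design supplies one: the patient's own untreated value. Section 11 does not use it within patients. Two separate summaries, one untreated and one on drug, each carry the full between-patient spread in starting level. The quantity the primary objective asks about, how far a patient's marker moved, has no stated SD or interval.

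Two drafting matters add to this. An analyst who follows the label in Section 1.2.1 could take day 1 of cycle 2 or 3 as baseline, and that is an on-drug value from the previous dose level. A laboratory that follows the Appendix C Syk sentence would not assay the pretreatment platelets, and an untreated value cannot be recovered after the first dose.

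The point does not reach BTK occupancy or plasma ibrutinib. In ibrutinib-naive patients their untreated values are nil by nature, so the level is already the effect against no drug. Nor does it concern the clinical endpoints or the contrasts between doses.

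**Working it through.** **The plan's own figure.** Section 11 claims 80-88% power for occupancy with 10 to 12 patients (85% against 95%, SD 0.10, two-sided 0.05), and 95% with 8 patients (SD about 0.05, level 0.01). For a one-sample t-test, use the noncentral t with n − 1 degrees of freedom and noncentrality (0.95 − 0.85)/SD × √n.

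- n = 10: noncentrality 3.16, power 80.3%
- n = 11: noncentrality 3.32, power 84.8%
- n = 12: noncentrality 3.46, power 88.3%
- n = 8, SD 0.05, level 0.01: noncentrality 5.66, power 95.1%

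The figures reproduce. They concern occupancy only; the plan states no precision for change in any other marker.

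**Precision of change from untreated.** The documents give n = 12 but no SD for these markers and no correlation ρ between untreated and on-drug values. Results are therefore in units of the marker's SD, assumed equal before and on drug, over a range of assumed ρ. For the log-ratio analysis, read SD as the SD of the log level.

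- From two separate summaries, treated as independent: half-width = t(0.975, 2n − 2) × √(2/n). At n = 12, 2.074 × 0.408 = 0.85 SD, whatever ρ is.
- Paired: SD of change = √(2(1 − ρ)), and half-width = t(0.975, n − 1)/√n × √(2(1 − ρ)). At n = 12 the first factor is 2.201/3.464 = 0.635. At ρ = 0.5 the second is 1.00, giving 0.64 SD.

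| n | Separate summaries | Paired, ρ 0.1 | ρ 0.3 | ρ 0.5 | ρ 0.7 |
|---|---|---|---|---|---|
| 12 | 0.85 | 0.85 | 0.75 | 0.64 | 0.49 |
| 10 | 0.94 | 0.96 | 0.85 | 0.72 | 0.55 |
| 8 | 1.07 | 1.12 | 0.99 | 0.84 | 0.65 |

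At n = 12 the two methods break even where √(2(1 − ρ)) = 0.847/0.635 = 1.33, that is, ρ of about 0.11. Below that, pairing gains nothing.

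**Platelet Syk, passages side by side.** Section 8.10 and footnote g include the pretreatment measurement. The Appendix C assay sentence names only the 24-hour samples. The Appendix C tube list draws a yellow-top tube pre-dose, at 24 hours after day 1 and at 24 hours after day 28. That matches the platelet schedule, although the text never assigns the tube to platelets. The sample is therefore probably drawn; what is in doubt is whether it is assayed for Syk.

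**The case against.** The strongest reply is that the untreated comparison is not lost. If levels are tabulated by draw, the time-zero mean stands beside the on-drug means. With complete data, the difference of those means equals the mean within-patient change. This stands. A reader might infer that the effect against no drug goes unestimated, or that three similar on-drug means could not be told apart from no effect. The documents do not support that, because the untreated summary is a fourth figure that shows direction and size. What is missing is the paired SD and interval. If only medians are reported, a difference of medians is not a median change.

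Second, the Section 11 sentence does not exclude changes, since a change is itself a continuous variable, and Appendix C plainly intends changes and decreases. This too stands, and it narrows the gap to an unnamed reference and statistic.

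Third, a reader might turn this into a power claim. At n = 12 and a true shift of 0.8 SD, an unpaired test has 47% power and a paired one 71% at ρ = 0.5. But the plan proposes no unpaired test, and both the shift and ρ are assumed. At a shift of 1.5 SD the figures are 94% and 99.7%. The power contrast should not be charged to the plan.

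Fourth, the Syk mismatch may be shorthand. The plasma paragraph of Appendix C also lists only 4 and 24 hours, although Section 8.6 includes a pre-dose sample. It would be wrong to say that the trial has no Syk baseline, since two schedules require one. The passages still disagree, and the value cannot be recovered once missed.

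Fifth, change from cycle 1 day 1 does not isolate each dose. Every patient takes 420, 280, then 140 mg. The drug is an irreversible inhibitor, and the protocol expects total BTK to decline on treatment. This is correct and must be stated with the results. Level summaries share the limit, so it is no reason to leave out the paired change.

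**Conclusion.** The concern holds in a limited form. For chemokines, BTK mRNA, total and phospho-BTK, downstream proteins, NF-κB and platelet Syk, the plan collects the right reference sample but does not name it as the reference or specify a within-patient analysis. Direction and size of change can be read from separate summaries; their within-patient precision cannot. At n = 12 the paired interval is narrower by 0.10, 0.21 and 0.36 SD at ρ of 0.3, 0.5 and 0.7 (0.85 less 0.75, 0.64 and 0.49), with nothing gained at ρ of about 0.1. This assumes equal SDs, complete pairs and a ρ that the documents do not give. The need for a named reference does not depend on ρ, because Section 1.2.1 applies the baseline label to on-drug days.

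The Syk mismatch is a separate small contradiction, cheap to settle before the first patient is dosed. Neither part touches the occupancy test or its power. A reader might infer that the repaired analysis would give a clean effect for each dose; under the fixed descending order it cannot.

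**What to change.** In Section 11, for these markers:

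1. Name the cycle 1 day 1 pre-dose sample as the reference, and limit the baseline label in Section 1.2.1 to it.
2. Report the within-patient log change for each cycle as a geometric mean ratio with 95% CI.
3. Choose one lead time point, for example the 24-hour draw after day 28, which exists for both the blood markers and Syk. Keep the other draws and the level summaries as support. Without a lead time point, each blood marker would have 5 on-drug draws × 3 cycles = 15 ratios.
4. State a rule for values below quantification, since a log ratio is undefined at zero.
5. State that the cycle 2 and 3 changes combine current dose with time on treatment and earlier dosing.

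In Appendix C, reconcile the Syk sentence with Section 8.10 and footnote g so that the pretreatment platelets are assayed.

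The cost is wording in Sections 11 and 1.2.1 and one sentence in Appendix C. It needs no new visit, draw or tube, and the only assay affected is already required by Section 8.10 and footnote g. The downside is that a patient without a usable pretreatment sample drops out of that marker's change analysis, so the number of pairs should be reported with each ratio.

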12 REPORTING REQUIREMENTS

Please see Appendix B.

13 CONFIDENTIALITY PLAN

All data will be entered in PDMS/CORE.

Appendix A. IWCLL categories of response in CLL.

Parameter	CR*	PR*	PD*
Group A			
Lymphadenopathy†	None > 1.5 cm	Decrease \geq 50%	Increase \geq 50%
Hepatomegaly	None	Decrease \geq 50%	Increase \geq 50%
Splenomegaly	None	Decrease \geq 50%	Increase \geq 50%
Blood lymphocytes	< 4000/ μ L	Decrease \geq 50% from baseline	Increase \geq 50% over baseline
Marrow‡	Normocellular, < 30% lymphocytes, no B-lymphoid nodules. Hypocellular marrow defines CRi (5.1.6).	50% reduction in marrow infiltrate, or B-lymphoid nodules	
Group B			
Platelet count	> 100 000/ μ L	> 100 000/ μ L or increase \geq 50% over baseline	Decrease of \geq 50% from baseline secondary to CLL
Hemoglobin	> 11.0 g/dL	> 11 g/dL or increase \geq 50% over baseline	Decrease of > 2 g/dL from baseline secondary to CLL
Neutrophils‡	> 1500/ μ L	> 1500/ μ L or > 50% improvement over baseline	

Group A criteria define the tumor load, group B criteria define the function of the hematopoietic system (or marrow).

*CR (complete remission): all of the criteria have to be met, and patients have to lack disease-related constitutional symptoms; PR (partial remission): at least two of the criteria of group A plus one of the criteria of group B have to be met; SD is absence of progressive disease (PD) and failure to achieve at least a PR; PD: at least one of the above criteria of group A or group B has to be met.

†Sum of the products of multiple lymph nodes (as evaluated by CT scans in clinical trials, or by physical examination in general practice).

‡These parameters are irrelevant for some response categories.

Appendix B. Reporting requirements.

These guidelines will be followed for the recording and reporting of adverse and serious adverse events.

1. Baseline events will be recorded in the medical history section of the case report form and will include the terminology event name, grade and start date of the event.
 - a. Baseline events are any medical condition, symptom, or clinically significant lab abnormality present before the informed consent is signed.
 - i. Hematologic laboratory abnormalities will not be recorded as baseline events for patients with acute leukemia, myelodysplastic syndrome, chronic lymphocytic leukemia, or chronic myeloid leukemia in blast phase.
 - ii. If exact start date is unknown, month and year or year may be used as the start date of the baseline event.
2. The maximum grade of the adverse event will be captured per course of protocol defined visit date.
3. These adverse events will be recorded in the case report form:
 - a. Any grade adverse event that is possibly, probably or definitely related to the study drug(s).
 - b. All serious adverse events regardless of attribution to the study drug(s).
 - c. Any grade adverse event regardless of attribution to the study drug(s) that results in any dose modification.
4. Hematologic adverse events will not be recorded or reported for studies in patients with acute leukemia, myelodysplastic syndrome, chronic lymphocytic leukemia, or chronic myeloid leukemia in blast phase except for:
 - a. Prolonged myelosuppression as defined by the NCI-CTCAE criteria specific for leukemia, e.g., marrow hypocellularity on day 42 or later (6 weeks) from start of therapy without evidence of leukemia (<5% blasts), or that results in dose modifications, interruptions or meets the protocol definition of dose limiting toxicity (DLT) or serious adverse event (SAE).
5. Serious adverse events will be reported according to institutional policy.
6. Protocol specific language regarding the recording and reporting of adverse and serious adverse events will be followed in the event of discordance between the protocol and Leukemic-specific adverse event recording and reporting guidelines.

Serious Adverse Event Reporting (SAE) for M. D. Anderson-Sponsored Protocols

An adverse event or suspected adverse reaction is considered “serious” if, in the view of either the investigator or the sponsor, it results in any of the following outcomes:

- Death
- A life-threatening adverse drug experience – any adverse experience that places the patient, in the view of the initial reporter, at immediate risk of death from the adverse experience as it occurred. It does not include an adverse experience that, had it occurred in a more severe form, might have caused death.

- Inpatient hospitalization or prolongation of existing hospitalization
- A persistent or significant incapacity or substantial disruption of the ability to conduct normal life functions.
- A congenital anomaly/birth defect.

Important medical events that may not result in death, be life-threatening, or require hospitalization may be considered a serious adverse drug experience when, based upon appropriate medical judgment, they may jeopardize the patient or subject and may require medical or surgical intervention to prevent one of the outcomes listed in this definition. Examples of such medical events include allergic bronchospasm requiring intensive treatment in an emergency room or at home, blood dyscrasias or convulsions that do not result in inpatient hospitalization, or the development of drug dependency or drug abuse (21 CFR 312.32).

- Important medical events as defined above, may also be considered serious adverse events. Any important medical event can and should be reported as an SAE if deemed appropriate by the Principal Investigator or the MDACC IRB.
- All events occurring during the conduct of a protocol and meeting the definition of a SAE must be reported to the IRB in accordance with the timeframes and procedures outlined in “The University of Texas M. D. Anderson Cancer Center Institutional Review Board Policy for Investigators on Reporting Unanticipated Adverse Events for Drugs and Devices”. Unless stated otherwise in the protocol, all SAEs, expected or unexpected, must be reported to the MDACC IRB, regardless of attribution (within 5 working days of knowledge of the event).
- **All life-threatening or fatal events**, that are unexpected, and related to the study drug, must have a written report submitted within **24 hours** (next working day) of knowledge of the event to the MDACC IRB.
- Unless otherwise noted, the SAE log will be utilized for safety reporting to the MDACC IRB.
- Serious adverse events will be captured from the time of the first protocol-specific intervention, until 30 days after the last dose of drug, unless the participant withdraws consent. Serious adverse events must be followed until clinical recovery is complete and laboratory tests have returned to baseline, progression of the event has stabilized, or there has been acceptable resolution of the event.
- Additionally, any serious adverse events that occur after the 30 day time period that are related to the study treatment must be reported to the MDACC IRB. This may include the development of a secondary malignancy.

Reporting to FDA:

- Serious adverse events will be forwarded to FDA by the MDACC IRB according to 21 CFR 312.32.

It is the responsibility of the PI and the research team to ensure serious adverse events are reported according to the Code of Federal Regulations, Good Clinical Practices, the protocol guidelines, the sponsor's guidelines, and Institutional Review Board policy.

Investigator Communication with Supporting Companies: N/A

Reporting of External SAEs

The MDACC institutional policy for reporting of external SAEs will be followed.

